1.3. HUMAN PAPILLOMAVIRUS VACCINATION AND EU ACTION

On 10 April 2008, the European Parliament adopted a resolution on combating cancer in the enlarged EU, and Council conclusions on reducing the European burden of cancer were adopted on 10 June 2008. The resolution recommended the 'cost-effective integration of appropriate HPV testing for cervical cancer screening and HPV vaccination to protect young women from cervical cancer'. The Vaccine European New Integrated Collaboration Effort (VENICE) and the European Cervical Cancer Association reports show that currently over half of the EU countries do not have vaccination programmes. The remaining member states vaccinate girls only.

1.4. GAPS IN THE LITERATURE

The vaccination of girls only may not protect males, especially if herd immunity is not achieved due to incomplete uptake of the vaccine in girls. Therefore, in view of the recent rise in HPV-oropharyngeal carcinoma, some experts are raising the possibility of the vaccination of boys as well as girls. Yet, to date insufficient data is available on oropharyngeal HPV infection to allow the accurate assessment of the need for and cost effectiveness of including boys in the HPV vaccination programmes in the EU.

Furthermore, there is little information on the prevalence of HPV infection in the mouth in the general population or on the age and gender distribution of this infection. The data that is available consists of small studies. These are usually retrospective and most of the study cohorts are over ten years old – therefore most of the prevalence data available is at least ten years old. Furthermore, the studies used a variety of sample types and different HPV detection techniques. Therefore the results are widely varying with reported HPV prevalence rates in the mouth between 0% and 31%.

Table 1: Frequency with which high-risk HPV types were detected in oral exfoliated cell samples using PCR methods (> 10 cases).

Study	City	Period of patient accrual	Age range	HPV detection	Type of oral sample	No of samples	HPV+ rate
D'souza 2007	Baltimore, USA	2000-5	<50yrs-34%, >50yrs-66%	PCR	Oral rinse and brush	200	6%
Smith 2007	Iowa , USA	n/a	2-20	PCR	Oral exfoliated cells	1235	1.9%
Rintala 2006	Finland	N/A	28	PCR	Scrapings	462	15-27%
Smith 2004	Iowa, USA	1994-97	18-70, 34% <55	PCR	Oral exfoliated cells	333	10.8%
Summersgill 2001	Iowa	<2001	<20	PCR	Swabs or oral rinses	268	8.7% <7yrs, 0% 7-12, 5.2% 13-20
Koch 1997	Denmark	<1997	0-17	PCR	Oral rinses	392	0.26%
Puranen 1996	Finland	1981-96	0.3-11.6	PCR	Oral scrapings	98	31.6%
Rice 1996	London	<1996	3-11	PCR	Buccal swabs	267	17%
Jennison 1990		<1990	preschool	PCR	Oral scrapings	21	24%

Table 2: Frequency with which high-risk HPV types were detected in tonsillectomy samples using PCR methods (> 10 cases).

Study	Year	City	Period of patient accrual	Age range	HPV detecti on	Number of samples	Number positive for HPV
Klinkenberg	2010	Netherlands	1997-98	29.2	PCR	195	2 (1%)
Ernster	2009	USA	1979-82; 1997- 2001	> 21 years	PCR	226	0 (0%)
Kim	2007	Korea	1995-2005	NS	RT-PCR	69	3 (4%)
Sisk	2006	USA	AO	paediatric patients	PCR	50	1 (2%)
Ribeiro	2006	Brazil	NS	2-13 years	PCR	64	5 (7.8%)
Mammas	2006	Greece	1995-2000	2-14 years	PCR	106	6 (5.7%)
Chen	2005	Sweden	2001-02	23.2 years	PCR	206	13 (6.3%)
Strome	2002	USA	1987-95	52.5 years	PCR	48	0 (0%)
Klussman	2001	Germany	"new cases"	52 years	PCR	14	0 (0%)

AO (abstract only): includes unspecified number of low-risk types; prevalence fell with increasing age from 11.5% in preschool children to 0% in older adults.

NS: Not Significant.

This data is essential for the assessment of the need for and cost effectiveness of including boys in the HPV vaccination programmes, and for the determination of the age of viral acquisition in the general population and hence the age of start of vaccination programmes (Kim,Vaccine 2008; Smith Pediatr Infect Dis J. 2007), as it may be that young people acquire earlier in the mouth than in the cervix, due to oral sex experimentation starting at a younger age than sexual intercourse. This data is also essential for the evaluation of the potential effectiveness of screening programmes, and preventative educational programmes (Pediatr Infect Dis J. 2007).

1.5. STUDY RATIONALE

There is little information on the distribution of HPV within the oropharynx and the reservoirs of infection within the mouth. Different studies show different rates for different sites within the oropharynx. However, since these studies use different types of samples and different HPV detection techniques, no reliable data can be surmised from them. Furthermore there is no data on the

effectiveness of vaccination for the prevention of HPV infection in the mouth, or on persistence of HPV infection in the mouth or the effect of HPV vaccination on HPV infection in the mouth. The study rationale is to gather data on the occurrence of HPV in the mouth and determine if it is common enough to implement a vaccination programme for boys as well.

2. AIMS, OBJECTIVES AND OUTCOME MEASURES

To provide current data on the prevalence, distribution and natural history of HPV infection in the mouth, which are essential requirements for the assessment, development and evaluation of cost-effectiveness of prophylactic vaccination and screening programmes.

2.1. OBJECTIVES

2.1.1. PRIMARY OBJECTIVE:

• To estimate the overall, age and gender specific prevalence of HPV in the oropharynx in patients undergoing tonsillectomy for non-malignant conditions

2.1.2. SECONDARY OBJECTIVES:

- To compare the HPV oropharynx prevalence between different sites—in order to identify the different reservoirs of HPV infection
- To describe the distribution of HPV seropositivity in the study population by age and gender
- To describe HPV-type distribution overall by age, gender, and sampling site
- To describe distribution by age and gender of patients who are both HPV PCR positive and anti-HPV L1 sero-positive – predicting persistent HPV infection
- To provide preliminary estimates of the clearance and persistence of HPV infection and antibodies in the oropharynx, as detected in follow-up oral fluid, finger tips/nail brushings and urine samples
- To assess the presence of anti-L1 HPV antibodies in saliva as a marker of vaccination or previous infection in the oral cavity
- To assess the presence of HPV in the urine
- To assess the presence of HPV in finger tips/nail brushings
- To provide preliminary evaluation of the performance of potential non-invasive tests for the detection of HPV infection in the mouth against HPV detection rates in tonsillectomy and oropharyngeal scrapes
- To identify the change in overall prevalence and distribution of HPV in tonsils over time, and to describe preliminary data on age and gender specific changes over time
- To provide preliminary data on the potential effect of HPV vaccination in the prevention of oral infection

2.2. OUTCOME MEASURES

2.2.1. PRIMARY OUTCOME

Occurrence of HPV in tonsil samples

[figure not shown]

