2.2.2. SECONDARY OUTCOME

- Occurrence of HPV in oral fluid, fingertip/nail brushings, oropharyngeal scrapes and urine samples
- Occurrence of HPV infection clearance in follow-up oral fluid, fingertip/nail brushings and urine samples collected at approximately 3 6 months after the first HPV positive sample
- Occurrence of persistent HPV infection in follow-up oral fluid, fingertip/nail brushings and urine samples collected at approximately 3 6 months after the first HPV positive sample
- Occurrence of HPV infection detected in follow-up oral fluid, fingertip/nail brushings and urine samples collected at approximately 3 6 months after the first HPV negative sample
- Occurrence of anti-HPV L1 antibodies in serum

Occurrence of anti-HPV L1 antibodies in oral fluid sample

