7. STUDY PROCEDURES AND SAMPLE COLLECTION

All samples should be collected in accordance to the study procedure manual developed by GSK with details of sample collection kits, volume of samples to be collected and storage temperature requirements.

For a patient to be eligible for inclusion in the data analysis, the following samples are a minimum requirement:

- Oral samples
- Blood
- Oropharyngeal brushings
- Tonsils

 After written consent is obtained, the patients (above 16 years old only) will complete a short study questionnaire including age, gender, history of tobacco/alcohol use, sexual history including age of start of sexual intercourse, lifetime numbers of sexual partners, engagement in oral sex and lifetime number of oral sex partners etc.

- 2. An HPV vaccination history will also be taken. Consent/assent will also be taken from the patient, parent(s) or their guardian(s), if applicable, to obtain the patient's HPV vaccination status from vaccine and medical health records from their GP and/or other relevant health and educational authorities. The data requested will include confirmation of HPV vaccination status, including dates, number of doses and the type of vaccine given.
- 3. Oral fluid samples will be collected for HPV PCR and HPV antibody tests, using an oral rinse and an exudate collection device respectively.
- 4. A 20 30 ml urine sample will be collected for HPV PCR test.
- 5. Blood serum will be taken for HPV and biomarker serology tests. This can be taken after the patient has been anaesthetised if necessary. 20 mls of blood will be taken from patients aged 16 years and above, 10 mls from patients below 16 years old.
- 6. Once the patient is anaesthetised, two brush cytology scrapings using cytobrushes (provided) will be taken: one from the posterior pharynx including above and below the soft palate so that the adenoidal area is included, and a second separate brush scrape will be taken from the back of the tongue (base of tongue).
- 7. Tonsillectomy will then be performed and the tonsillar tissue will be placed in 10% buffered formalin and sent to the pathology department for paraffin embedding according to a specific protocol.
- 8. Stratified sampling will be employed to ensure that sufficient numbers of patients are recruited from all age groups, especially the age groups between 10 and 20 years old.

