12.2. ANALYSIS OF OUTCOME MEASURE

The statistical analyses will be described in detail in a statistical analysis plan (SAP). All of the tests will be two-sided with an alpha level of 0.05.

12.2.1. PRIMARY OUTCOME:

The overall prevalence will be estimated as the number of patients with HPV detected in tonsils divided by the total number of patients with available samples. An exact 95% confidence interval will be computed. The prevalence per age and gender group will be calculated similarly.

The relationship between prevalence and age will be explored using logistic regression with the age as a continuous covariate and gender and centre as categorical covariate. The number of degrees (one, two, three) of the model and possible variable transformation (e.g. log-transformation of age) could be determine based on graphical analysis of prevalence versus age relationship and on model fit criteria (e.g. AIC).

12.2.2. SECONDARY OUTCOME:

The overall prevalence will be estimated as the number of patients with HPV detected in oral fluid, oropharyngeal scrapes and urine samples divided by the total number of patients with available samples. An exact 95% confidence interval will be computed.

The prevalence per age and gender group will be calculated similarly. Prevalence rate will be compared among centres using a Cochran-Mantel-Haenszel test with stratification by age group.

Relationship between the prevalence of HPV in tonsils and the prevalence of HPV in oropharyngeal scrapes, oral fluid, and urine samples will be analysed by computing kappa coefficient. Specificity, sensitivity, positive predictive value and negative predictive value of HPV detection in the different sample types will be derived using the oral sample results as the reference.

Relationship between presence of anti-HPV L1 antibody in oral fluid samples and occurrence of HPV in tonsils and/or in oropharyngeal scrape samples will be analysed by computing kappa coefficiency. Specificity, sensitivity, positive predictive value and negative predictive value of anti-HPV L1 antibody assay will be derived using the oral sample results as the reference.

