The rate of HPV persistence will be calculated as the proportion of baseline HPV-positive patients who again test HPV-positive in oral fluid, fingertip/nail brushings and urine samples collected after approximately 3 - 6 months. The rate of oral HPV infection clearance will be calculated as the proportion of baseline HPV-positive patients who test HPV-negative in oral fluid, fingertip/nail brushings and urine samples collected after approximately 3 - 6 months.

HPV incidence will be calculated as the proportion of baseline HPV-negative patients who test HPV positive in oral fluid, fingertip/nail brushings and urine samples collected after approximately 3 - 6 months. Exact 95% confidence intervals will be computed.

Multi variable regression models will be used to calculate the odds ratios of different risk factors for having HPV DNA in the tonsil and in the oropharynx, Variables to be included in the model (e.g. serological markers and clinical risk factors such as HPV vaccination status, tobacco and alcohol use) will be selected on the basis of descriptive statistics/possible causal relationship and/or a stepwise approach. Analysis of results may be performed to identify a possible marker or combination of markers for screening for persistent HPV infections in the oropharynx.

Among females in the target age class for vaccination (12 to 24 years), exploratory analyses will compare the HPV prevalence rate in HPV vaccinated and non HPV vaccinated patients using a Fisher's exact test. Association between HPV vaccine and oral HPV infection will be assessed using a case-control approach. Cases will be patients with HPV positive oral sample and controls will be patients with HPV negative oral sample. The exposure to vaccine will be compared between the case and the control groups using logistic regression, OR and its 95% confidence interval will be derived.

Prevalence of HPV in tonsils will be described and compared between the current cohort and the comparison historical cohort using a Cochran-Mantel-Haenszel test with stratification by age group and gender.

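### The primary objective is HPV prevalence in the oropharynx, but the primary outcome and estimator count tonsil tissue only, and no planned prevalence estimate combines tonsil with the oropharyngeal scrapes

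*Protocol*

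**What the plan says.** - **Objective (Protocol 2.1.1, repeated in the Study Summary):** "To estimate the overall, age and gender specific prevalence of HPV in the oropharynx in patients undergoing tonsillectomy for non-malignant conditions".
- **Primary outcome (2.2.1):** "Occurrence of HPV in tonsil samples".
- **Primary estimator (12.2.1):** "the number of patients with HPV detected in tonsils divided by the total number of patients with available samples", with an exact 95% confidence interval, and likewise by age and gender.
- **Other sites as secondary outcomes (2.2.2):** "Occurrence of HPV in oral fluid, fingertip/nail brushings, oropharyngeal scrapes and urine samples". Section 12.2.2 gives prevalence for these sample types (nail brushings are not named there) and a kappa against the tonsil result.
- **What is collected (Section 7):** two brush scrapings besides the tonsil. The posterior one is described as "one from the posterior pharynx including above and below the soft palate", and the text adds that this is meant to take in the adenoidal area. The second is from the base of the tongue. Oropharyngeal brushings and tonsils both belong to the minimum sample set for inclusion in the analysis.
- **How the protocol regards the sites:** Section 1.5 notes that reported rates vary between sites within the oropharynx. The first secondary objective compares sites to find reservoirs. The models in 12.2.2 are for "risk factors for having HPV DNA in the tonsil and in the oropharynx".
- **One place where sites are combined:** 12.2.2 relates oral-fluid antibody to HPV in tonsils and/or scrapes.

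**The concern.** The objective names a region and the estimator measures one part of it. A patient who is tonsil-negative but positive at the base of the tongue has HPV in the oropharynx and is counted as negative in the primary analysis. The protocol does not say that tonsil tissue stands in for the whole region, and its own text treats the sites as potentially different.

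This matters because Section 1.5 gives the purpose as finding out whether HPV in the mouth is frequent enough to justify extending vaccination to boys. If the primary result is read under the label of the objective, it is a lower bound presented as an estimate. The objective, outcome and estimator are all fixed in this document and disagree here, so the matter is not one of detail left to the SAP.

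**Working it through.** **The plan's own figures.** The protocol gives no any-site prevalence and no between-site overlap, so there is nothing of that kind to reproduce. The precision example in 12.3 (8.4 to 11.8% at an observed 10%) concerns sampling error, not which site is counted. It matches an exact interval for 1250 patients; for 925 the exact interval is 8.1 to 12.1%. That is a separate matter and plays no part below.

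**Direction.** Let T be tonsil-positive and S be positive on either scrape, in the same patients. Every T-positive patient is also positive for T or S, so

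p(T or S) = p(T) + p(S) − p(T and S) ≥ p(T).

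Equality holds only if every scrape-positive patient is also tonsil-positive.

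**Bounds when overlap is unknown.** max(pT, pS) ≤ p(T or S) ≤ min(1, pT + pS).

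**Inputs.**
- pT: crude pool of Table 2. Positives are 2 + 0 + 3 + 1 + 5 + 6 + 13 + 0 + 0 = 30. Samples are 195 + 226 + 69 + 50 + 64 + 106 + 206 + 48 + 14 = 978. 30/978 = 3.1%. Individual studies range from 0 to 7.8%.
- pS: the protocol has no figure for scrapes alone. Section 12.3 quotes 6.5% for oral HPV and 31% for scrapes and oral washings taken together. Using either for the scrapes is an assumption.

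**Results (illustrative).**

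| Tonsil | Scrapes (assumed) | Any site, full nesting | Any site, no overlap | Tonsil as share of any site |
|---|---|---|---|---|
| 3.1% | 6.5% | 6.5% | 3.1 + 6.5 = 9.6% | 3.1/9.6 = 32% to 3.1/6.5 = 48% |
| 3.1% | 31% | 31% | 3.1 + 31 = 34.1% | 3.1/34.1 = 9% to 3.1/31 = 10% |
| 7.8% | 6.5% | 7.8% | 7.8 + 6.5 = 14.3% | 7.8/14.3 = 55% to 100% |

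The last row takes the highest tonsil figure in Table 2 and shows that the gap can vanish. The documents therefore fix the direction but allow anything from no gap to roughly tenfold.

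**Is the any-site figure planned anywhere?** Section 12.2.1 covers tonsil only. The prevalence paragraph of 12.2.2 covers oral fluid, scrapes and urine, without tonsil. The antibody paragraph of 12.2.2 forms a tonsil and/or scrape status, but only for kappa and accuracy measures against antibody. No prevalence of that status, overall or by age and gender, is planned.

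**The case against.** Several points on the other side are sound.

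- **Tonsil is a declared and defensible primary outcome.** It is an oropharyngeal site, the numerator is openly labelled as tonsil, and tonsil is the only tissue in the historical comparison group (7.2), for which the power calculation was made. A reader might infer that the wrong outcome was chosen. The documents do not support that; only the objective's wording and the missing estimate are at fault.
- **The information is not lost.** Scrape prevalence is reported with an exact interval and by age and gender, together with kappa against the tonsil. If kappa were computed on the same patients with the two scrapes treated as one result, a reader could work back to the overall any-site figure. No kappa by age or gender is stated, so the age- and gender-specific part of the objective would remain unanswered.
- **Sites are combined once.** It is tempting to say that no analysis combines them. The antibody agreement analysis in 12.2.2 does. What is absent is a prevalence estimate.
- **A scrape-only positive is not always oropharyngeal.** The posterior brush deliberately takes in the adenoidal area, so not every such patient shows the primary figure to be too low, and a tonsil-or-scrape composite could itself overstate oropharyngeal prevalence.
- **The numbers are weak.** The 6.5% is not a scrape figure, the 31% includes washings, and the Table 2 pool mixes ages, countries and periods and includes one abstract that counted low-risk types. Section 1.5 itself warns against relying on comparisons across such studies.

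These points limit the harm. They do not remove the mismatch, because no planned prevalence estimate answers the primary objective as worded.

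**Conclusion.** The point stands as a mismatch between objective and estimator. As written, the primary analysis estimates HPV prevalence in tonsil tissue. For prevalence at any sampled site in the same patients it is a lower bound: it may equal that figure and cannot exceed it.

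The size of the shortfall cannot be derived from the protocol, because overlap between sites is not given. The ranges of 6.5 to 9.6% and 31 to 34% against 3.1% rest on assumed scrape prevalences and on literature from different populations and assays. A reader might take them as evidence that the tonsil figure will capture only a third to a half, or a tenth, of oropharyngeal prevalence. The documents do not support such a claim. They support only the direction, and the fact that a substantial gap is possible.

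**What to change.** 1. Reword the primary objective in 2.1.1 and the Study Summary to prevalence of HPV in tonsil tissue, overall and by age and gender. Leave 2.2.1 and 12.2.1 as they are, so the tonsil outcome still serves the historical comparison.
2. Add to 12.2 a prevalence of HPV in tonsil or either oropharyngeal scrape, overall and by age and gender, with an exact 95% confidence interval.
3. Define its denominator as patients with tonsil and both scrape results. Section 7 sets a minimum sample set while 12.2.1 divides by patients with available samples, so the denominator needs stating.
4. State that the posterior brush includes the adenoidal area, and report tonsil or base of tongue as a stricter oropharyngeal version.

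The cost is wording and a little extra tabulation. Both sample types are already in the minimum set, so no new samples are needed. The downside is that the composite mixes formalin-fixed tissue with surface brushings, which Table 3 sends to partly different laboratories. This should be said alongside the estimate.

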2.2.2. SECONDARY OUTCOME

- Occurrence of HPV in oral fluid, fingertip/nail brushings, oropharyngeal scrapes and urine samples
- Occurrence of HPV infection clearance in follow-up oral fluid, fingertip/nail brushings and urine samples collected at approximately 3 6 months after the first HPV positive sample
- Occurrence of persistent HPV infection in follow-up oral fluid, fingertip/nail brushings and urine samples collected at approximately 3 6 months after the first HPV positive sample
- Occurrence of HPV infection detected in follow-up oral fluid, fingertip/nail brushings and urine samples collected at approximately 3 6 months after the first HPV negative sample
- Occurrence of anti-HPV L1 antibodies in serum

Occurrence of anti-HPV L1 antibodies in oral fluid sample

3. STUDY DESIGN

OROMOUTH is a prospective, multi-centre, cross sectional study.

4. ELIGIBILITY CRITERIA

4.1. INCLUSION CRITERIA

The following patients are eligible:

1. Patients undergoing tonsillectomy for non-cancer reasons including operations for: recurrent tonsillitis, snoring surgery or obstructive sleep apnoea

- 2. Age 0 to 65 years
- 3. Patient, parent(s) or legal guardian(s) has given informed written consent

